## 5. SUPPORTING MORBIDITY AND MORTALITY ANALYSES

These endpoints will provide additional supporting analyses to aid interpretation of the morbidity and mortality data. These analyses may include events included in the heart failure expanded definition and/or heart failure equivalent events, as defined in Section 2, as appropriate for the endpoint.

The analyses of the focused endpoints will be based on descriptive statistics, nominal two-sided 95% confidence intervals and p-values. No statistical adjustment for multiple comparisons will be made.

These analyses are intended to support any updated labeling for patients with heart failure.

### 5.1. Cardiovascular Mortality and Heart Failure Morbidity N

These two endpoints are similar to the primary and first focused endpoint, except they also include the following hospitalization equivalent events: Hospital-based observation unit and unscheduled clinic visits.

#### 5.1.1. Rate of CV Mortality and HF Hospitalization / Hospitalization Equivalent

The objective is to demonstrate that treatment with the BAROSTIM NEO System, relative to medical management, reduces the rate of cardiovascular mortality or worsening heart failure that leads to any of the following events:

- Hospitalization for heart failure OR
- Emergency room visit for heart failure OR
- Hospital-based observation unit for heart failure OR
- Unscheduled clinic visit for heart failure OR
- Cardiac assist device OR
- Heart transplant

#### 5.1.2. Rate of CV Mortality and HF Hospitalization / Hospitalization Equivalent (Expanded Definition)

The objective is to demonstrate that treatment with the BAROSTIM NEO System, relative to medical management, reduces the rate of cardiovascular mortality or worsening heart failure that leads to any of the following events:

- Hospitalization for heart failure (expanded definition) OR
- Emergency room visit for heart failure (expanded definition) OR
- Hospital-based observation unit for heart failure (expanded definition) OR
- Unscheduled clinic visit for heart failure (expanded definition) OR
- Cardiac assist device OR

- Heart transplant

The expanded definition is defined in the CEC Charter and includes hospitalizations that are determined to be heart failure hospitalizations by a CEC consensus yet may not have all of the documentation available.

## 5.2. M&M endpoints with follow-up ending at 6, 12 and 24 months

Over the course of follow-up in the trial, there were many unexpected changes that occurred in patient care that could confound the evaluation of the benefit of Barostim therapy. These include the approval and adoption of pharmaceutical and device-based treatments for heart failure (e.g., ARNI, SGLT2, Cardiac Contractility Modulation), as well as changes in care patterns and practices due to COVID-19. To better understand the impact of these event, the analyses on the morbidity and mortality endpoints will be repeated assuming that follow-up stops at 6 months, 12 months and 24 months. The same endpoint definitions as described above and analysis methods in Section 2.1.4 will be repeated while censoring follow-up time and events at 6, 12, and 24 months.

## 5.3. Alternative Statistical Methods for Analyzing Rates

To further incorporate the impact of the timing that the events occur over follow-up, alternative methods of analysis on the endpoints will be performed. These will include, at a minimum, the Anderson Gill method for recurrent events, and semi-parametric joint frailty models (JFM).

The JFM analysis is intended to aid the interpretation of the primary negative binomial model analysis by providing insight into the contribution of censoring events and recurrent heart failure hospitalization events to the overall (marginal) treatment effect estimated by the negative binomial model analysis. This JFM has a demonstrated ability to provide unbiased estimate of the treatment effect on recurrent heart-failure hospitalizations in the presence of dependent censoring (i.e., censoring being more likely in subjects at higher risk of heart-failure hospitalization). In the JFM, the dependence of censoring and recurrent events is accounted for by a frailty term, which measures a patient-specific tendency to have an increased likelihood of both types of events. The model assumes that a patient's censoring and recurrent events are independent of each other after conditioning on the frailty term. The JFM will be implemented using piecewise constant hazards for the recurrent events and censoring events. This method may be implemented by Gaussian quadrature using SAS PROC NLMIXED24. Piecewise constant hazard time intervals will be defined prior to performing analyses comparing treatment arms. For each hazard ratio comparing the two arms, a 95% confidence interval and p-value will be calculated using the Wald method. The JFM analysis will be repeated with only death as a dependent censoring event and transplant/LVAD as non-informative censoring events.

#### 5.4. Reduction of the Components of the Endpoint

The objective is to demonstrate that treatment with the BAROSTIM NEO System, relative to medical management:

- Reduces the rate of hospitalizations for heart failure\*
- Reduces the rate of hospitalizations for heart failure\* or emergency room visits for heart failure
- Reduces cardiovascular mortality
- Reduces LVAD or heart transplant
- Reduces LVAD
- Reduces heart transplant
- Reduces cardiovascular mortality, LVAD or heart transplant

\*May include hospitalization equivalent events, as well as heart failure events using the expanded definition.

For the analyses that include hospitalizations and hospitalization equivalent events only, the primary analysis will be a semi-parametric frailty model (as described in Section 4.2) that adjusts for the competing risk of the censoring events (e.g., cardiovascular mortality and/or LVAD and/or heart transplant).

For the analyses that include censoring events only, the analyses will be evaluated descriptively with Kaplan-Meier time-to-event methods. The event date will be the date of censoring event. Living subjects will be censored at the date of last contact. Subjects that die due to non-cardiovascular causes will be censored at the date of death. The estimate of survival and corresponding 95% log-log confidence interval as well as the number of subjects at risk and number of subjects that die will be presented at 6 months, 12 months, 24 months, and annually thereafter. The hazard ratio between arms and its 95% confidence interval will be estimated by a proportional hazard's regression model.

#### 5.5. Win Ratio – M&M Only

A Win Ratio analysis will be performed using the components of the morbidity and mortality endpoints with the following hierarchy.

1. CV Death
2. Heart transplant or LVAD
3. Number\* of hospitalizations for Heart Failure

The Win Ratio analysis will use all pairs of subjects between the two study arms to determine the number of wins and losses for the treatment versus control arm.

For each pair, follow-up is defined by the shorter of the follow-up periods. For example, if one patient has 1 year of follow-up and the 2nd has 2 years, the follow-up time used for comparison is 1 year. If the first subject in a pair is censored prior to an event time

for the second subject in a pair, that pair is a tie. This produces the shared duration of follow-up for each pair, avoiding bias due to differential follow-up.

The p-value comparing the two arms will be calculated using the Schoenfeld-Finkelstein method. A 95% confidence interval for the Win Ratio will be calculated using the bootstrap method.

#### **5.6. Win Ratio Expanded – HF Therapy**

A Win Ratio analysis will be performed using the components of the morbidity and mortality endpoints as well as intensification of therapeutic interventions for heart failure. This analysis will follow the same methodology as the Win Ratio above. The following hierarchy will be used:

4. CV Death
5. Heart transplant or LVAD
6. Number of hospitalizations for Heart Failure
7. Intensification of therapeutic interventions for heart failure as defined in Table 3.

#### **5.7. Reduction in Time Spent CV Death / HF Hospitalization**

Reduction of the percent of follow-up time spent either dead from a cardiovascular cause and/or in the hospital for worsening heart failure between the two arms.

This analysis will be performed over all follow-up time, and at 6-, 12- and 24- months follow-up time.

#### **5.8. Clinical Stability**

The clinical stability endpoint categorizes subjects as “improved”, “Stayed the same” or “worsened” based on their mortality status, heart failure hospitalization status and NYHA class at 12 months. The number of HF hospitalization (HFH) in the 12 months prior to enrollment will be compared to the subjects’ post randomization HFHs through 12 months. A subject with less than 12 months follow-up will not be evaluable for this endpoint unless the subject died or experienced more HFH during follow-up as compared to the pre-enrollment 12 months (i.e., “worsened”). A subject will be classified as “worsened” if either the subject died prior to 12 months, the subject experienced more HFH through 12 months follow-up than the pre-enrollment 12 months, OR the subject has a higher NYHA class at 12 months as compared to baseline. A subject will be classified as “improved” if the subject did not worsen AND either had fewer HFH through 12 months follow-up as compared to pre-enrollment 12 months OR had an improvement in NYHA class at 12 months. A subject who neither worsened nor improved and who is evaluable on all 3 parameters through 12 months will be classified as “stayed the same”. The p-value comparing the two arms will be calculated using the proportional odds method assessing a shift in the distribution of the ordinal outcome. A

95% confidence interval for the proportional odds will be calculated using the bootstrap method.

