## 3. PROTOCOL

### 3.1. Trial Summary

The BAROSTIM NEO - Baroreflex Activation Therapy for Heart Failure is a prospective, randomized trial in subjects with reduced ejection fraction heart failure. Subjects will be randomized in a 1:1 ratio to receive Barostim Activation Therapy with an implanted BAROSTIM NEO System in addition to medical management or to receive medical management alone (no device implant). The trial will be conducted at up to 120 investigational centers in the U.S. and up to 20 investigational centers outside the U.S. These centers will enroll up to 1200 subjects to randomize approximately 480 subjects who meet the entry criteria.

A single center will not be permitted to randomize more than 15% of the total number of randomized subjects. A subject will be considered enrolled when he or she has provided written consent.

Post-consent screening measurements will be obtained only after the subject has completed a medication optimization and 4-week medication stabilization period. For all subjects, the heart failure medication regimen must remain stable during the 4-week medication stabilization period, except for minor adjustments (see inclusion criterion #5 in section 3.3.1). Subjects will be randomized when they have met all enrollment criteria and after all baseline measurements have been obtained.

Prior to randomization, site personnel will be required to provide an anticipated implant date. For subjects randomized to the Medical Management Arm, this date will be used for the timing of all other trial visits. For subjects randomized to the Device Arm, trial visits will be based on the actual date of device implant.

Device subjects will have the device activated prior to being discharged from the hospital, and should remain at the hospital for at least 2 hours post-programming for observation prior to being discharged. At the physician's discretion subjects may remain overnight for observation to evaluate programming.

For all subjects, trial visits will occur at 0.5, 1, 1.5, 2, 3, 6, 9 and 12 months post-implant (post anticipated implant for medical management). Visits will occur quarterly from 15 to 24 months and semi-annually thereafter.

Subjects are followed in an identical manner regardless of trial arm.

Figure 7 provides a schematic of the overall trial design.

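### Inclusion in the clinical stability analysis (SAP 5.8) depends on the outcome: subjects who leave alive before 12 months can count only as worsened, a modest bias whose direction is not fixed

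*SAP*

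**What the plan says.** SAP 5.8 classifies each subject from mortality, heart failure hospitalizations (HFH) and NYHA class. There are three routes to worsened: death before 12 months, more HFH through 12 months than in the 12 months before enrollment, or that "the subject has a higher NYHA class at 12 months as compared to baseline". Improved requires that worsening is absent and that one of two conditions is met, namely that the subject "had fewer HFH through 12 months follow-up as compared to pre-enrollment 12 months OR had an improvement in NYHA class at 12 months". The middle category, stayed the same, takes those in neither group, provided that all three parameters can be assessed through 12 months.

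The evaluability rule for short follow-up is that such a subject "will not be evaluable for this endpoint unless the subject died or experienced more HFH during follow-up" than before enrollment, and such a subject is then worsened.

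The arms are compared by the "proportional odds method assessing a shift in the distribution of the ordinal outcome". The introduction to SAP section 5 reports these analyses with "nominal two-sided 95% confidence intervals and p-values", adds that "No statistical adjustment for multiple comparisons will be made", and says they are meant to support updated labeling.

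Section 5.8 gives no imputation, weighting or sensitivity analysis for the excluded subjects, and does not ask for their number by arm.

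**The concern.** A subject who leaves alive at month 7 with no excess HFH is removed from numerator and denominator. The same subject with excess HFH stays in, in the worst category. No early leaver can enter as improved or unchanged.

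This would matter little if exits were rare or equal in the two arms. Neither is assured. Allocation is equal ("Subjects will be randomized in a 1:1 ratio"), but the control arm has no implant, so subjects know their assignment. Protocol 3.12 lists receipt of the device where it is market approved as a reason for withdrawal, a route that mainly concerns control subjects. SAP 4.3 itself treats differing withdrawal as a possible source of bias. With unequal exits, two arms with identical true outcomes can show different category shares, and the result would carry a nominal p-value into a labeling discussion.

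**Working it through.** The plan gives no expected category shares, power or dropout rate for this endpoint, so there is no stated figure to reproduce. The check is of direction and size.

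**Formula.** Let d be the share of an arm that leaves alive before 12 months, Wc the share worsened among everyone else, and w the share of leavers with excess HFH before leaving. Under 5.8:

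observed share worsened = [(1−d)·Wc + d·w] / [(1−d) + d·w]

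This exceeds Wc by d·w·(1−Wc) / [(1−d) + d·w], which is never negative and, for w above 0, rises with d.

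**Exit unrelated to outcome.** Assumed: Wc = 30% in both arms, exits 15% versus 5%.

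| w | 15% exits | 5% exits | Gap (points) | Odds ratio for worsening |
|---|---|---|---|---|
| 0 | 30.0% | 30.0% | 0 | 1.00 |
| 10% | 0.270/0.865 = 31.2% | 0.290/0.955 = 30.4% | 0.85 | 1.04 |
| 20% | 0.285/0.880 = 32.4% | 0.295/0.960 = 30.7% | 1.66 | 1.08 |
| 30% | 0.300/0.895 = 33.5% | 0.300/0.965 = 31.1% | 2.43 | 1.12 |

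The last row is a ceiling. It needs every worsening to be visible before exit, which cannot happen while some worsening is defined by NYHA class at 12 months.

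**Base case.** With 40% of worsening seen before exit, w = 0.4 × 30% = 12%:
- 15% exits: 0.273/0.868 = 31.5%
- 5% exits: 0.291/0.956 = 30.4%, a gap of 1.0 point
- 20% exits: 0.264/0.824 = 32.0%, a gap of 1.6 points against 5%

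**Simulation.** One million subjects per setting, with the SAP 8.1 values: 0.4 events per patient-year, 0.18 terminal, and 1.7 used as a gamma shape. Assumed: prior-year HFH rate 0.6, NYHA worse in 10% and better in 40%, exit times uniform over the year. With exit unrelated to outcome, true worsening was 27.8%. Observed worsening was 28.2%, 29.2% and 30.2% at 5%, 15% and 25% exits. Observed improvement fell from 45.9% to 45.3% to 44.7%.

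Put back into the formula with Wc = 27.8%, these results imply an effective share seen of just under 0.4, which is the source of the 40% above. It is an effective value: only about 7% of simulated leavers had excess HFH, against about 25% who would have worsened. The rest of the inflation arises because subjects who die first stay in the analysis.

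With prior-year rates of 0.3 and 1.0, the gap in worsening between 15% and 5% exits was 0.95 and 0.76 points.

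**Exit related to outcome.** When exit probability rose strongly with frailty (prior rate 0.6), observed worsening was only 28.0%, 28.2% and 28.5% at the three exit rates. Observed improvement still fell, from 45.7% to 44.7% between 5% and 15% exits.

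More generally, let T be true worsening in the whole arm and v the share of leavers who would have worsened. Then observed = [T − d·v + d·w] / [(1−d) + d·w]. With T = 34.5% in both arms, w = 10% and exits 15% versus 5%:
- v = 40%: 0.300/0.865 − 0.330/0.955 = +0.1 points
- v = 50%: 0.285/0.865 − 0.325/0.955 = −1.1 points
- v = 60%: 0.270/0.865 − 0.320/0.955 = −2.3 points

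The documents contain one mechanism of this kind. Protocol 3.15 requires withdrawal of subjects who receive an assist device or transplant. Neither event appears in the 5.8 definition of worsened, so without excess HFH these subjects become non-evaluable, which flatters their arm.

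**Scale.** With 319 subjects (SAP section 1), about 160 per arm, the standard error of a difference in shares near 30% is √(2 × 0.3 × 0.7 / 160) = 5.1 points. A 1-point bias is about one fifth of that.

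**The case against.** The strongest reply is that leaving active follow-up is not the same as having under 12 months of follow-up. Partial withdrawal (Protocol 3.4.5) continues collection of hospitalizations and deaths from records. Subjects lost to follow-up may stay in the database for any available data (Protocol 3.13). Telephone visits were allowed during COVID-19 (SAP 7). A subject with HFH known through 12 months can still be classed as improved on fewer HFH. Early exit may also be uncommon: SAP Table 2 lists 18 of 259 previously randomized subjects (6.9%) as contributing interim data only, over both arms and without a breakdown by reason or exposure. The ingredients are also analyzed elsewhere by methods that use partial follow-up: Kaplan-Meier estimates (5.9, 5.10), joint frailty models (5.3) and repeated-measures NYHA (6.1).

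All of this stands, and it limits the size. It does not remove the asymmetry for subjects whose follow-up does end early. The intention-to-treat analysis in SAP 4.3 moves the start of follow-up and leaves the 5.8 rule as it is. The imputation in SAP 3.2.2 covers only 12-month MLWHF for the win ratio.

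A reader might infer that the rule always penalizes the arm with more exits, and so favors the device if controls leave more often. The documents do not support that: they report no exits by arm, and the sign can reverse as shown. A reader might also infer a large distortion. Exits of 30% versus 5% with all worsening seen before exit would give 0.300/0.790 − 0.300/0.965 = 6.9 points, but nothing in the documents suggests such exit rates, and full visibility is ruled out by the 12-month NYHA route.

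**Conclusion.** The concern holds in a limited form. SAP 5.8 makes inclusion depend on the outcome, and no other part of the plan repairs it. With exit unrelated or only moderately related to outcome, the arm with more early exits shows an inflated share worsened: about 1 point at 15% versus 5% exits, and roughly 1 to 2.5 points across plausible assumptions, the top of that range being a ceiling. With strongly outcome-related exit, or assist-device and transplant withdrawals without excess HFH, the bias shrinks or changes sign. The exit rates, the 30% true worsening and the share seen before exit are all assumptions. Deaths before 12 months are handled properly. The primary endpoint and its alpha are untouched. This is a low-cost improvement to one unadjusted supporting analysis, worth making because that analysis is meant to inform labeling.

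**What to change.** Amend SAP 5.8 as follows:
- Keep every subject with post-activation follow-up in the analysis.
- Count deaths before 12 months and documented excess HFH as worsened, as now.
- State explicitly how assist-device and transplant withdrawals are classified for this analysis, so that they do not drop out as non-evaluable.
- For the remaining early leavers, multiply impute the 12-month category from arm, baseline and 6-month NYHA class, HFH to date and follow-up time. Inverse-probability-of-follow-up weights are an alternative.
- Report subjects non-evaluable under the current rule by arm and reason, and keep the current rule as a sensitivity analysis.

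The cost is SAP wording and modest programming with data already collected. The drawback is reliance on a missing-at-random assumption, which the counts by arm and reason would help a reader to judge.

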### **3.15. Cardiac Assist Device or Heart Transplant**

Subjects in either treatment arm who progress in their heart failure status to receive either a cardiac assist device or a heart transplant must be withdrawn from the study. For subjects with an active BAROSTIM NEO device in geographies where the device is not approved, the device must be permanently turned off prior to the cardiac assist device or heart transplant procedure (see Section 3.10). The investigator should discuss the options for either leaving the IPG in place or for explanting the IPG including the potential risks of each. It is recommended that the Carotid Sinus Leads should not be explanted, and the leads should be left implanted with the leads capped. These device subjects must be followed for 30 days after the termination of device therapy or after the explanting of any of the BAROSTIM NEO System.

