#### 4.3.1. Rate of Cardiovascular Mortality and Heart Failure Morbidity

The endpoint is to demonstrate that treatment with the BAROSTIM NEO System, relative to medical management, reduces the rate of cardiovascular mortality or worsening heart failure that leads to hospitalization or emergency room visit, cardiac assist device or heart transplant.

Subjects will be censored at the time of a terminal event (i.e., death, permanent cardiac assist device, heart transplant, or novel implantation of a device to receive Cardiac Contractility Modulation) or end of follow-up, whichever occurs first. Subjects who progress in their heart failure status to receive either a cardiac assist device or a heart transplant must be withdrawn from the study within 60 days of the assist device procedure or heart transplant (see Section 3.15).

Definitions for the endpoint components can be found in Section 4.3.4. The events will be adjudicated in a blinded manner by an independent Clinical Events Committee (CEC). The CEC Charter definitions supersede any definitions in this protocol.

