## 3. PRIMARY AND FOCUSED ENDPOINTS

### 3.1. Primary Endpoint: Rate of CV Mortality and HF Morbidity

#### 3.1.1. Rate of Cardiovascular Mortality and Heart Failure Morbidity

The objective is to demonstrate that treatment with the BAROSTIM NEO System, relative to medical management, reduces the rate of cardiovascular mortality or worsening heart failure that leads to hospitalization or emergency room visit, cardiac assist device or heart transplant.

Subjects will be censored at the time of a terminal event (i.e., death, permanent cardiac assist device, heart transplant, or novel implantation of a device to receive Cardiac Contractility Modulation) or end of follow-up, whichever occurs first.

The end of follow-up for analysis of morbidity and mortality will occur on the last date where adverse event status is known for the subject. This definition of follow-up time ensures that only time periods where morbidity and mortality status has

been assessed are included. End of follow-up is defined for each subject as the later date of:

- Last study visit
- Last date of adverse events reported in the database:
  - If last adverse event is a hospitalization, use discharge date
  - If last event is not a hospitalization, use resolution date if resolved, else use onset date
- Date subject completed the final, protocol defined end of study visit (note: this only occurs at end of study)

This end of follow-up date will be used to calculate follow-up time for the negative binomial model.

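### SAP 5.8 does not score a cardiac assist device or heart transplant before 12 months as worsened, so survivors whose hospitalization count has not risen are normally not evaluable (minor)

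*SAP*

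**What the plan says.** SAP 5.8 sorts subjects into improved, stayed the same or worsened "based on their mortality status, heart failure hospitalization status and NYHA class at 12 months". There are three routes to worsened. The first two apply "if either the subject died prior to 12 months, the subject experienced more HFH through 12 months follow-up than the pre-enrollment 12 months"; the third applies if "the subject has a higher NYHA class at 12 months as compared to baseline". The evaluability rule reads: "A subject with less than 12 months follow-up will not be evaluable for this endpoint unless the subject died or experienced more HFH during follow-up" than in the 12 months before enrollment. Neither list names an assist device or a transplant. The arms are compared by a proportional odds method.

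Three other provisions decide what happens to a subject who has one of these procedures:

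- Protocol 3.15: subjects who progress "to receive either a cardiac assist device or a heart transplant must be withdrawn from the study".
- Protocol 4.3.1: such subjects "must be withdrawn from the study within 60 days of the assist device procedure or heart transplant".
- SAP 3.1.1, for the morbidity and mortality endpoint: "Subjects will be censored at the time of a terminal event (i.e., death, permanent cardiac assist device, heart transplant", and so on through the list, or at the end of follow-up if that is earlier.

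SAP 5.8 does not define follow-up for its own purposes.

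**The concern.** Assist device and transplant are components of the primary composite. The win ratio hierarchies (SAP 3.2.2, 5.5, 5.6) place them directly below cardiovascular death and above heart failure hospitalizations, and the rationale in 3.2.2 says this order reflects seriousness. In 5.8 the order breaks down: one hospitalization more than in the prior year makes a subject worsened, while a transplant alone can leave the subject without a category.

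The loss is informative, because these subjects become not evaluable through progression of their heart failure. An arm with more of these procedures loses more of its worst outcomes and looks better than it should. If the device prevents such procedures, the analysis understates its benefit. If they are more frequent in the device arm, the analysis flatters the device. SAP 5.3 recognises dependent censoring and models it for event rates; 5.8 has no comparable protection. Section 5 says its analyses are intended to support updated labeling.

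**Working it through.** SAP 5.8 gives no sample size, power or rate for this endpoint, so there is no planned figure to reproduce. The check is to apply the rule as written and then gauge scale.

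**1. Follow-up ends at the procedure (the SAP 3.1.1 convention).** Take a subject alive at 12 months with an assist device or transplant before then. Follow-up is under 12 months and the NYHA route is closed, so only the HFH comparison remains.

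| Prior-year HFH | 0 HFH after | 1 after | 2 after | 3 after |
|---|---|---|---|---|
| 0 | not evaluable | worsened | worsened | worsened |
| 1 | not evaluable | not evaluable | worsened | worsened |
| 2 | not evaluable | not evaluable | not evaluable | worsened |
| 3 | not evaluable | not evaluable | not evaluable | not evaluable |

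Example: one prior HFH, one HFH at month 3, an elective device implant at month 5. The comparison is 1 against 1, so the subject is not evaluable. Some subjects start above zero by design: Protocol 3.3.1, criterion 4, requires a heart failure hospitalization (an emergency room visit may count) in the past 12 months when NT-proBNP is below 400 pg/ml.

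**2. Follow-up taken to a 12-month visit held before withdrawal (the alternative convention).** The 12-month window in Protocol Table 6 is 360 ± 45 days, that is days 315 to 405. A procedure on day 330 with withdrawal up to 60 days later reaches day 390, inside the window. The rule then gives:

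- more HFH than before, or higher NYHA: worsened;
- otherwise, fewer HFH or better NYHA: improved;
- equal HFH and unchanged NYHA: stayed the same.

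Steps 1 and 2 are alternatives. They cannot both apply to the same analysis.

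**3. Does other wording close the gap?** The introduction to SAP Section 5 allows heart failure equivalent events where appropriate. SAP 5.1 names these as observation unit stays and unscheduled clinic visits, so neither procedure is covered.

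**4. Scale (illustration only).** Inputs: 319 subjects (SAP Section 1), taken as 159.5 per arm; control rate 0.4 per patient-year and relative reduction 0.35 (SAP 8.1); probability that an event is a censoring event, 0.18 (SAP 8.1). Expected first-year terminal events per arm = n × (1 − exp(−rate × p)).

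- Control: 159.5 × (1 − exp(−0.4 × 0.18)) = 11.1
- Treatment: 159.5 × (1 − exp(−0.4 × 0.65 × 0.18)) = 7.3
- Total: about 18

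Over the SAP's own scenario ranges (rate 0.35 to 0.45, p 0.1 to 0.3), with the 35% effect, the total runs from 9 to 34.

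The documents do not say what share of terminal events are assist devices or transplants; I assume 10% to 50%. For the fraction not scored as worsened I use a simulation with subject rates drawn from a gamma distribution of shape 1.7 and mean 0.4, prior HFH drawn from the same rate, and 30% of subjects entering by the route that requires a prior hospitalization, so that about half have a prior HFH. It gives 53-54% not scored if the device or transplant admission itself counts as an HFH, and 92% if it does not.

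- Low: 18.4 × 0.10 × 0.53 = 1.0
- High: 18.4 × 0.50 × 0.92 = 8.5

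This is roughly 1 to 8 subjects across both arms.

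**The case against.** The strongest case against is that this is one supporting scale with nominal p-values, deliberately built on three parameters, and that few subjects are affected. That stands, and it is why the point is minor. Entry criteria exclude Stage D heart failure and active transplant evaluation and cap NT-proBNP at 1600 pg/ml, which makes a high first-year share of these procedures less likely. The 10-50% share and the prior-HFH inputs are assumptions, and the simulation does not use the SAP's own prior-event parameter (beta of 1.8).

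Three further objections limit the claim.

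- **Some of these subjects are still scored.** The HFH definition in Protocol 4.3.4 lists mechanical heart failure therapy among qualifying treatments. A non-elective device admission that meets the other criteria can raise the count and give worsened, but an elective one cannot, and one extra HFH may only equal the prior-year count. A death before 12 months after the procedure, if captured, also gives worsened. A reader might infer that every such subject is lost; the text does not support that.
- **Harm is not hidden.** A reader might infer that an arm imbalance would go unseen. It would not: the primary endpoint (3.1), the focused win ratio (3.2.2), the component analyses (5.4), two further win ratios (5.5, 5.6) and time to first event by type (5.9) all count or rank these events by arm.
- **A larger count does not follow from the base case.** Applying the control rate to everyone gives 319 × 0.4 × 0.18 = 23 terminal events, but that assumes no treatment effect.

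The CEC Charter and main SAP are not available and might add something. The Charter governs event definitions, including whether a device admission is an HFH, but 5.8 does not refer to either document for its scoring rule.

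**Conclusion.** The gap is real on the text and minor in weight. As written, SAP 5.8 makes a survivor of an assist device or transplant before 12 months not evaluable unless the HFH count exceeded the prior-year count. If follow-up is instead taken to a 12-month visit before withdrawal, a late procedure could be scored as stayed the same or improved. Either result conflicts with the SAP's own ranking of these events, and the exclusion can move the proportional odds estimate in either direction.

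The reading in step 1 assumes that the SAP 3.1.1 censoring rule governs follow-up in 5.8. The figure of 1 to 8 subjects is illustrative: it rests on the base-case rate, the 35% effect, the assumed 10-50% share and the simulated 53-92%. The conclusion rests on the rule and would stand at a different count. The primary endpoint is unaffected.

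**What to change.** In SAP 5.8, extend the first worsened criterion so that it covers a subject who *died, or received a permanent cardiac assist device or heart transplant, prior to 12 months*. Add the same two events to the exception in the 12-month evaluability rule. Every not-evaluable cell in the table above then becomes worsened, and a late procedure can no longer be scored as stayed the same or improved. Report the number of not-evaluable subjects by arm and reason.

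The cost is one sentence of SAP text, a small table, and a small change to the definition of the composite, which should be acknowledged as such. No new data are needed: the events are already part of the primary endpoint, and Protocol 3.4.5 has sites collect them even under partial withdrawal.
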